5.4 Dose-Determination Process

5.4.1 Dose-Determination Phase Segment 1 (Open-Label)

Dose-finding decisions including selection of dose levels for cohorts, determination of the MTD, RD, and stopping enrollment, as applicable, will be performed by the DRC. The key principles guiding DRC recommendations for dose levels in dose-finding are to ensure that patients receive treatment at therapeutic exposures and to sequentially increase the dose of CORT125281 in combination with enzalutamide as tolerated.

Dose escalation or de-escalation will occur only after review of data from each cohort by the DRC. All available data from patients receiving study drug will be used in dose escalation decisions. In addition, AEs occurring after the first cycle and ongoing PK assessment will be considered in dose escalation decisions.

There will be a 28-day DLT-evaluation period (from the first dose of CORT125281 through the completion of Cycle 1). The DLT-Evaluable Population will include all patients in the Dose-Determination Phase cohorts who receive at least 1 dose of CORT125281 and fulfill at least one of the following:

- Complete at least 28 days of continuous treatment with CORT125281 + enzalutamide and received at least 75% of the study regimen
- Experience a DLT

Patients who are non-evaluable for DLTs will include the following:

- Received <75% of the study regimen for reasons other than toxicity
- Patients who withdraw from the study prior to completion of Cycle 1 for reasons other than toxicity (eg, lost to follow-up, withdrawal of consent, or disease progression)

Patients who are non-evaluable for DLTs will be allowed to continue in the study and receive CORT125281 in combination with enzalutamide. Patients who experience toxicities requiring dose modification during the Lead-In Period may continue the study, with appropriate dose modification of enzalutamide and agreement of the Investigator and Medical Monitor but will be considered non-evaluable for DLTs. Patients who are non-evaluable for DLTs may be replaced to allow a sufficient number of evaluable patients per cohort.

A minimum of 3 evaluable patients in each cohort must complete 28 days of continuous combination treatment with enzalutamide and CORT125281 and have safety data reviewed by the DRC (described in Section 9.9) prior to proceeding to the next dose level. If <33% of the DLT-evaluable patients have experienced a DLT, then enrollment may proceed in the next cohort. If $\geq 33\%$ of the DLT-evaluable patients have experienced a DLT in a cohort, (with a minimum of 6 evaluable patients if 1 DLT is observed), the previous dose will be considered for the MTD or dose de-escalation will occur by approximately 20% from the current dose (with rounding allowed to account for available capsule strengths [Table 1]).

The CORT125281 dose for Cohort 1 of the Dose-Determination Phase Segment 1 will be 180 mg BID. Dose escalation of CORT125281 will initially be in up to doubling steps until any DLT or Grade 2 toxicity attributed to CORT125281 is reported; thereafter, dose escalation will be in $\leq 50\%$ steps. The starting dose for the subsequent cohort will be per the DRC recommendation and will be based upon tolerability and observed toxicity in previous cohorts (including DLTs), human PK, PD markers of target engagement, projected efficacious exposures, and the available capsule strengths. The DRC may adjust the dose of enzalutamide in subsequent cohorts based on PK and tolerability. The dose-escalation scheme is presented in Table 7.

Table 7 CORT125281 Dose Escalation and Reduction Scheme for Dose-Determination Segment 1

Dose Level	CORT125281 Dose (mg/day)
-1	280 mg/day
1 (Starting dose)	360 mg/day
Subsequent cohorts, until any DLT or Grade 2 toxicity attributed to CORT125281 is reported	Increase the dose by up to 100% (double the dose in the previous dose level)
Following any dose level with a DLT or Grade 2 toxicity attributed to CORT125281	Increase the dose in the most recent dose level by $\leq 50\%$

DLT, dose-limiting toxicity.

The enzalutamide dose for Cohort 1 of Dose-Determination Phase Segment 1 will be 160 mg daily during the Lead-In and Combination Treatment Periods. The enzalutamide dose in subsequent cohorts may be increased or decreased based on safety, PK, and tolerability. The Mean Ratio enzalutamide (ENZ) + M2 is the ratio of enzalutamide + M2 metabolite exposure concurrently administered with CORT125281 on Cycle 2 Day 1 divided by enzalutamide + M2 metabolite exposure on Cycle 1 Day -1. The Mean Ratio ENZ + M2 will be considered when assessing the effects of potential drug-drug interactions and determining the dose of enzalutamide for each cohort. While the DRC will consider the totality of the data and the variability that may occur with the small sample size in making their recommendations, a Mean Ratio ENZ + M2 < 0.75 or > 1.4 will be considered indicative of a notable interaction and support increasing or decreasing the dose of enzalutamide accordingly to achieve target exposures to approximate enzalutamide 160 mg daily.

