5.3 Timing of Study Treatment Administration

5.3.1 Dose-Determination Phase Segment 1 (Twice-Daily Dosing of CORT125281)

Patients in Dose-Determination Phase Segment 1 will take CORT125281 BID beginning on Cycle 1 Day 1 (every 12 hours \pm 3 hours) unless otherwise specified ([Table 3](#)), with the first dose occurring in the morning. It is recommended that if a patient misses a scheduled dose of CORT125281 and less than 6 hours have passed since the scheduled dosing time, the dose should be taken immediately. It is recommended that if more than 6 hours have passed since the scheduled dosing time, the patient should not take the missed dose, but should wait and take the next regularly scheduled dose. A window of at least 6 hours should be maintained between doses.

Alternative dosing schedules for CORT125281 dosing may be evaluated. If alternative schedules are evaluated, the total daily dose of CORT125281 will not exceed that projected to provide an exposure (AUC_{0-24} and C_{max}) of 1.5-fold the previous dose level.

Enzalutamide will be taken once a day, starting on Day -28 (Lead-In Period) and continuing through the combination period ([Table 3](#)) and, unless otherwise specified, should be taken in the morning. After completion of Cycle 2, enzalutamide may be dosed in the evening, if preferred by the patient or recommended by the Investigator.

The treatment schema for Dose-Determination Phase Segment 1 is summarized in [Table 3](#).

Table 3 Treatment Schema for Dose-Determination Phase Segment 1

Cycle Study Treatment	Lead-In Period	Combination Treatment Period
	Days –28 to –1	Days 1 to 28
Cycle 1 CORT125281 Enzalutamide	No dose taken Once a day	Twice a day Once a day
Cycle 2 – End CORT125281 Enzalutamide	N/A N/A	Twice a day Once a day

N/A, not applicable.

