6.6 Pharmacokinetic Measures

The plasma concentration data for CORT125281, CORT125324 (metabolite of CORT125281; $K_i > 10$ μ M at the GR), enzalutamide, M2, and enzalutamide carboxylic acid (inactive metabolite of enzalutamide) will be analyzed using non-compartmental methods to obtain estimates of standard PK parameters.

- Dose-Determination Phase Segment 1

- Lead-in Period: Plasma samples will be collected over a 24-hour period on the day prior to initiating CORT125281 to determine the PK parameters of enzalutamide and major metabolites.
- Combination Treatment Period: Plasma samples will be collected to assess the PK profile of CORT125281, enzalutamide, and their major metabolites to determine steady-state CORT125281 PK parameters and to assess the effect of CORT125281 on exposure to enzalutamide.
 - Cycle 1 Day 1
 - Cycle 1 Day 22 (partial profile)
 - Cycle 2 Day 1
 - Cycle 2 Day 15 and Cycle 3 Day 1 (partial profile)
- Dose-Determination Phase Segment 2
 - Combination Treatment Period: Plasma samples will be collected to assess PK parameters of CORT125281 and enzalutamide.
 - Cycle 1 Day 15
 - Day before second dose escalation (eg, Cycle 2 Day 1 or Cycle 2 Day 15)
- Expansion Phase:
 - Food-Effect Subcohort (10 patients in the Abi-Resistant Cohort):
 - Cycle 1 Day -7 and Day 1: Plasma samples will be collected to determine CORT125281 PK parameters
 - All patients in the Expansion Phase: Plasma samples to be collected on Cycle 2 Day 1 and Cycle 3 Day 1 to determine the concentration of CORT125281, enzalutamide, and their major metabolites.

Refer to the SoAs in [Table 20](#) (Dose-Determination Phase Segment 1), [Table 21](#) (Dose-Determination Phase Segment 2), and [Table 22](#) (Expansion Phase) for the timing and frequency of all PK sample collections.

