CORT125281 & Enzalutamide	Cycle 1 Day 1	0 hour, pre-dose	Within 15 minutes before the morning dose of study treatment
		30 minutes	Within 5 minutes of nominal time
		1 hour	
		1.5 hours	
		2 hours	±10 minutes
		3 hours	
		4 hours	
		6 hours	
		8 hours	
		12 hours	±30 minutes
		24 hours ^a , pre-dose	

PK Sample	Day	Nominal Time	Window
CORT125281 & Enzalutamide	Cycle 1 Day 22	0 hour, pre-dose	Within 15 minutes before the morning dose of study treatment
		2 hours	±10 minutes
CORT125281 & Enzalutamide	Cycle 2 Day 1	0 hour, pre-dose	Within 15 minutes before the morning dose of study treatment
		30 minutes	Within 5 minutes of nominal time
		1 hour	
		1.5 hours	
		2 hours	±10 minutes
		3 hours	
		4 hours	
		6 hours	
		8 hours	
		12 hours	±30 minutes
CORT125281 & Enzalutamide	Cycle 2 Day 15	0 hour, pre-dose	Within 15 minutes before the morning dose of study treatment
		2 hours	±10 minutes
CORT125281 & Enzalutamide	Cycle 3 Day 1	0 hour, pre-dose	Within 15 minutes before the morning dose of study treatment
		2 hours	±10 minutes
CORT125281 ^b	Intra-patient dose escalation: On current dose and 4 weeks following dose adjustment	0 hour, pre-dose	Within 15 minutes before the morning dose of CORT125281
		2 hours	±10 minutes
Enzalutamide ^b	Intra-patient dose escalation: On current dose and 4 weeks following dose adjustment	0 hour, pre-dose	Within 15 minutes before the morning dose of enzalutamide
		2 hours	±10 minutes

Note: On all days with pharmacokinetic assessments, CORT125281 and enzalutamide should be taken at the same time in the clinic. Both the times of the previous day's doses of CORT125281 and enzalutamide and the times of the current day's doses should be recorded.

^a. The Cycle 1 Day -1 24-hour enzalutamide sample and the Cycle 1 Day 1 pre-dose sample may be a single sample, if the timepoints align.

The Cycle 1 Day 1 24-hour sample should be taken prior to dosing on Cycle 1 Day 2.

^b. Patients who undergo intra-patient dose escalation of CORT125281.

Table 21 Pharmacokinetic Schedule of Assessments – Dose-Determination Phase Segment 2

PK Sample	Day	Nominal Time ^a	Window
CORT125281 & Enzalutamide	Cycle 1 Day 15	0 hour, pre-dose	Within 15 minutes before the dose of study treatment
		1 hour	±10 minutes
		2 hours	
		3 hours	
		4 hours	
		6 hours ^b	
CORT125281 & Enzalutamide	2 weeks (±2 days) after each dose escalation ^c	0 hour, pre-dose	Within 15 minutes before the dose of study treatment
		1 hours	±10 minutes
		2 hours	
		3 hours	
		4 hours	

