10.6. ECOG Performance Status

Data listing for ECOG performance status assessed at Screening, at each study visit, and at the EOT and EOT + 30 days visit will be provided for each patient. Patient performance status will also be summarized by treatment regimen dose group/arm and overall for each numeric grade at baseline and change from Baseline.

11. Pharmacokinetic Analyses

The plasma PK of exicorilant, enzalutamide, and major metabolites, including M2 will be characterized in the PK-Evaluable Population using noncompartmental analysis, and analyte concentration versus time plot will be provided. The following PK parameters will be calculated, whenever possible, from plasma concentrations of exicorilant, enzalutamide, and M2, and combined exposure to both enzalutamide and M2:

- AUC_{0-last} : Area under the plasma concentration-time curve calculated using linear trapezoidal summation from time 0 to time of last measurable concentration.
- AUC_{0-24} : Area under the plasma concentration-time curve from 0 to 24 hours, calculated using linear trapezoidal summation.
- AUC_{0-6h} : AUC values from time 0 to 6 hours post-dose.
- AUC_{0-inf} : Area under the plasma concentration-time curve from 0 to infinity, calculated as $AUC_{0-last} + C_{last} / \lambda_z$, where λ_z is the apparent terminal elimination rate constant (whenever possible).
- C_{max} : Maximum observed plasma concentration.
- C_{last} : Minimum concentration from time 0 to time of last measurable concentration.
- $C_{min,ss}$: Minimum observed plasma concentration, at predose at steady-state.
- CL/F : Apparent oral clearance.
- T_{max} : Time of the maximum plasma concentration (obtained without interpolation).
- T_{last} : Time after dosing of the last quantifiable concentration.
- λ_z : Terminal elimination rate constant (whenever possible).

Missing dates or times may be imputed for PK samples if the missing values can be established with an acceptable level of accuracy based on other information during the visit in question. If PK sampling for a given patient is not performed according to protocol instructions, the corresponding concentration data may be excluded from the PK analyses.

PK parameters will be tabulated and summarized by treatment at baseline and scheduled time points using descriptive statistics. PK relationship to measures of efficacy or toxicity may also be explored. Additional PK analyses may be performed as deemed appropriate.

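### Segment 1 first-day CORT125281 AUC0-24 and AUC0-last bridge an unsampled second dose, and AUC0-last covers unequal intervals on the two days of the enzalutamide interaction ratio

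*Protocol*

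**What the plan says.** **CORT125281 dosing and sampling.** Protocol Section 5.3.1: "Patients in Dose-Determination Phase Segment 1 will take CORT125281 BID beginning on Cycle 1 Day 1", every 12 h with a margin of 3 h either way. Table 20 samples Cycle 1 Day 1 at 0, 0.5, 1, 1.5, 2, 3, 4, 6, 8, 12 and 24 h. Its footnote adds: "The Cycle 1 Day 1 24-hour sample should be taken prior to dosing on Cycle 1 Day 2". Nothing is drawn between 12 h and 24 h, and the 12-h sample is not labelled pre-dose.

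**Planned parameters.** Protocol Table 15 and SAP Section 11 define AUC0-24 as "Area under the plasma concentration-time curve from 0 to 24 hours, calculated using linear trapezoidal summation". Both also list AUC0-last and AUC0-inf, and SAP Section 11 adds AUC0-6h. Neither lists AUC0-12 or an AUC over the dosing interval.

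**Enzalutamide ratio.** Enzalutamide is taken once daily. Protocol Section 5.4.1 defines the Mean Ratio ENZ + M2 as exposure on Cycle 2 Day 1 "divided by enzalutamide + M2 metabolite exposure on Cycle 1 Day -1" and sets limits: "a Mean Ratio ENZ + M2 < 0.75 or > 1.4 will be considered indicative of a notable interaction". No metric or time interval is given, and the SAP does not mention the ratio. For the denominator day, Protocol Section 6.6 states: "Plasma samples will be collected over a 24-hour period on the day prior to initiating CORT125281". For the numerator day, Table 20 stops at 12 h, although Section 6.6 does not mark Cycle 2 Day 1 as a partial profile.

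**The concern.** There are two separate problems.

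1. On Cycle 1 Day 1 the CORT125281 AUC0-24 and AUC0-last can be computed, so the SAP's qualifier that parameters are calculated whenever possible does not screen them out. But the last trapezoid joins the 12-h and 24-h samples, and the peak from the second dose lies between them. The 24-h concentration also contains drug from both doses, so it cannot inform the first dose's lambda-z or AUC0-inf.

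2. For enzalutamide, AUC0-24 cannot be obtained directly from the Cycle 2 Day 1 samples, and AUC0-last covers 24 h on Day -1 but 12 h on Cycle 2 Day 1. The ratio has action limits that "will be considered indicative of a notable interaction and support increasing or decreasing the dose of enzalutamide accordingly". An unnamed metric leaves open a choice that would fall below the lower limit when nothing has changed.

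At stake are the accuracy of a reported first-day exposure and the reproducibility of the interaction ratio. The ratio rests on few patients. Cohort 3 had no lead-in and so has no Day -1 profile, which leaves at most the 2 + 3 = 5 patients of Cohorts 1 and 2 who received the combination (Protocol Section 1.3.2.1).

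**Working it through.** The plan states no figure for either quantity, so there is nothing to reproduce. The check applies the planned trapezoids, at the Table 20 times, to a one-compartment oral model.

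**Inputs from the documents:** sampling times (Table 20); second dose at 9 to 15 h (Section 5.3.1); CORT125281 Tmax of 2.00 h fasted and 4.08 h fed (Section 1.3.2.1); ratio limits 0.75 and 1.4 (Section 5.4.1).

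**Assumptions, not in the documents:** CORT125281 half-life 3 to 24 h; enzalutamide half-life 12 to 200 h with Tmax 1 h and steady state on both days; M2 behaves within the same range.

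**Model.** For one dose, in units of bioavailable dose/volume: C(t) = ka/(ka − ke) × [exp(−ke·t) − exp(−ka·t)], with ke = ln 2/half-life and ka set to give the stated Tmax. Doses add.

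**A. CORT125281, Cycle 1 Day 1.** Worked case: half-life 6 h, Tmax 2 h, second dose at 12 h just after the sample. Then ke = 0.1155 and ka = 1.3416.

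- C(12) = 0.2736. C(24) = 0.3419, which contains both doses.
- Trapezoid, 12 to 24 h: 12 × (0.2736 + 0.3419)/2 = 3.693. True value: 8.064.
- 0 to 12 h: trapezoid 6.287, true 6.288.
- Estimated/true AUC0-24 = (6.287 + 3.693)/(6.288 + 8.064) = 9.980/14.352 = 0.70.

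Almost all the error comes from the final interval. Estimated/true over the assumed range:

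| Second dose at | Tmax 2.00 h, half-life 3 → 24 h | Tmax 4.08 h, half-life 3 → 24 h |
|---|---|---|
| 9 h | 1.12 → 0.98 | 1.00 → 0.99 |
| 12 h | 0.61 → 0.80 | 0.72 → 0.81 |
| 15 h | 0.70 → 0.88 | 0.86 → 0.91 |

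With the second dose at 12 h the shortfall is 1 − 0.81 = 19% to 1 − 0.61 = 39%. Across the window the result runs from 0.61 to 1.12 of true, so the error also differs between patients according to when they took the evening dose. AUC0-last has the same error when the 24-h sample is measurable.

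Remedy checked: with no dose before the 12-h sample, AUC0-12 on Cycle 1 Day 1 is 0.996 to 1.007 of true. At steady state, 2 × AUC0-12 is 0.999 to 1.007 of the true AUC0-24.

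**B. Enzalutamide ratio with no interaction (true ratio 1.00).** If AUC0-last were used, the numerator would be AUC0-12 and the denominator AUC0-24:

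| Half-life (h) | 12 | 24 | 48 | 96 | 140 | 200 | flat profile |
|---|---|---|---|---|---|---|---|
| AUC0-12/AUC0-24 | 0.652 | 0.580 | 0.541 | 0.521 | 0.514 | 0.510 | 12/24 = 0.500 |

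All values are below 0.75. To exceed 1.4, the true ratio would have to exceed 1.4/0.652 = 2.15 to 1.4/0.500 = 2.80. With AUC0-12 on both days the ratio is 1.00. It is also 1.00 if the Cycle 2 Day 1 pre-dose value stands in for the missing 24-h value, which requires steady state.

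**The case against.** **On the ratio, much of the objection stands.** A reader might infer that the plan divides a 12-h AUC by a 24-h AUC. Section 5.4.1 says only exposure. The 0 to 12 h samples are the same on both days, and AUC0-6h and Cmax, both listed in SAP Section 11, are already matched. Section 1.3.2.1 reports no clinically significant effect on enzalutamide exposure, which does not fit a ratio of 0.5 to 0.65. That suggests, without proving, that a mismatched ratio was not relied on. The same section attributes dropping the lead-in to that absence of an interaction, after an interim look at PK and safety, but does not name this ratio. Section 5.4.1 also has the DRC weigh all the data.

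**A reader might also infer that the sampling cannot support 24-h exposures at all.** It can on Cycle 2 Day 1, if steady state is assumed; the plan simply does not write the rule. On Cycle 1 Day 1, enzalutamide is unaffected, because it is once daily and has a 24-h sample.

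**Downstream harm is not shown.** A low first-day AUC would inflate an accumulation ratio, but neither document plans one. The 1.5-fold limit in Section 5.3.1 concerns projected exposure, and Section 1.5.2 justifies the Segment 2 doses from Segment 1 plasma concentrations without naming a visit or an AUC.

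**A single bias figure would be fragile.** Taking 4200 ng·h/mL a day at 180 mg BID and half of the simulated 137 ng/mL trough at 360 mg BID gives (2100 + 12 × 68.5)/4200 = 0.70. That assumes linear PK and a first day like steady state. Section 1.3.2.1 later reports a 2- to 4-fold rise on repeat dosing and more-than-proportional exposure. Hence only ranges are given here.

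**What survives:** the first-day CORT125281 AUC error, and an unnamed ratio metric alongside a listed parameter that covers unequal intervals.

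**Conclusion.** The first-day point holds. With an unsampled second dose, the planned CORT125281 AUC0-24 and AUC0-last on Cycle 1 Day 1 are about 19% to 39% too low when that dose is at 12 h, and 0.61 to 1.12 of true over the permitted window. These sizes rest on a one-compartment model and assumed half-lives of 3 to 24 h; they are not estimates for this trial. That the 24-h sample cannot serve the first dose's lambda-z or AUC0-inf follows from the dosing alone.

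The ratio point holds only conditionally. AUC0-24 is not directly available on Cycle 2 Day 1, and AUC0-last, if chosen, would give about 0.5 to 0.65 with no interaction (assumed half-life 12 h upward, including a flat profile). The documents do not show that it was chosen. They also do not show that the interaction conclusion, any accumulation estimate or the 1.5-fold limit was distorted.

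This is a correction to the PK derivation rules, worth making because it costs little.

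**What to change.** In SAP Section 11:

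- **CORT125281, Segment 1:** report AUC0-12 on Cycle 1 Day 1 and Cycle 2 Day 1. Give 2 × AUC0-12 as daily exposure on Cycle 2 Day 1 only, labelled as assuming steady state. Do not report AUC0-24 or a 24-h AUC0-last for Cycle 1 Day 1.
- **24-h sample on Cycle 1 Day 1:** exclude it from CORT125281 AUC and lambda-z for that day. Keep it for enzalutamide.
- **Early second doses:** use the recorded dose times (diary, Protocol Section 5.13) to flag patients whose second dose came before the 12-h sample, because their AUC0-12 is affected too.
- **Mean Ratio ENZ + M2:** define it on AUC0-12 on both Cycle 1 Day -1 and Cycle 2 Day 1, not on AUC0-last. State which metric was used for the interaction conclusion in Protocol Section 1.3.2.1.

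Cost: SAP wording and re-derivation from samples already scheduled. The downside is that there is no first-day AUC0-24 for CORT125281, and the 24-h figure on Cycle 2 Day 1 depends on steady state.

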5.4.2 Dose-Determination Phase Segment 2 (Double-Blind)

In Segment 2, all patients will start treatment with CORT125281 240 mg QD on Cycle 1 Day 1. Patients will continue on their current dose of enzalutamide during the Screening Period and at the initiation of CORT125281. Beginning on Cycle 1 Day 16, the dose of the investigational agent will be increased in 40-mg increments every 2 weeks, as tolerated, with either CORT125281 (Arm A; N=12) to a maximum dose of CORT125281 320 mg QD or with placebo (Arm B; N=4) (Table 8). If any planned dose escalation is postponed due to transient intolerable Grade 2 toxicity or scheduling conflicts (delays not due to toxicity), the dose may be escalated within 14 days of the planned escalation.

- Arm A (N=12): CORT125281 240 mg QD under fed conditions with upward dose titration in combination with enzalutamide. CORT125281 will be increased in 40-mg increments every 2 weeks (+14-day window) based upon tolerability to a maximum dose of 320 mg QD (Table 8).
 - Cycle 1 Day 1: CORT125281 240 mg QD
 - Cycle 1 Day 16 (+14-day window): CORT125281 280 mg QD
 - Cycle 2 Day 2 to Cycle 2 Day 16 (+14-day window): CORT125281 320 mg QD

- Arm B (N=4): CORT125281 240 mg QD under fed conditions, with an increase in the number of placebo capsules every 2 weeks (+14-day window) (Table 8).
 - Cycle 1 Day 1: CORT125281 240 mg QD
 - Cycle 1 Day 16 (+14-day window): CORT125281 240 mg QD
 - Cycle 2 Day 2 to Cycle 2 Day 16 (+14-day window): CORT125281 240 mg QD

Table 8 CORT125281 Upward Dose Titration for Dose-Determination Phase Segment 2

Dose Level	Resulting CORT125281 Dosage (QD)		Open-Label Bottle (CORT125281)	Blind-Label Bottle (CORT125281 or Placebo) ^a
	Arm A	Arm B		
1 (Starting Dose)	240 mg	240 mg	6 capsules	0 capsules
+1 (First Increase)	280 mg	240 mg	6 capsules	1 capsule
+2 (Second Increase)	320 mg	240 mg	6 capsules	2 capsules

QD, once daily.

Note: The CORT125281 dose will be escalated in 2-week intervals unless there are intolerable Grade 2 toxicities, dose-limiting toxicities, or Grade 3 or greater toxicities attributed to CORT125281 (Section 5.7).

^a. Note: The blind-label bottle contains blinded capsules (CORT125281 [Arm A] or placebo [Arm B]).

During the double-blind portion of the Dose-Determination Phase (ie, Segment 2), an unblinded Medical Monitor independent of the study team will provide additional oversight for the study, including review of serious unexpected AEs considered related to either CORT125281 or enzalutamide and DLTs.

The DLT-evaluation period will extend from the first dose of CORT125281 through the completion of Cycle 3. The DLT-Evaluable Population will include all patients in Segment 2 who received at least 1 dose of CORT125281 and fulfilled at least 1 of the following:

- Completed 3 cycles of treatment with CORT125281 + enzalutamide and received at least 75% of the study regimen
- Experience a DLT

Patients who are non-evaluable for DLTs will include the following:

- Received <75% of the study regimen for reasons other than toxicity
- Patients who withdraw from the study prior to completion of Cycle 3 for reasons other than toxicity (eg, lost to follow-up, withdrawal of consent, or disease progression)

Patients who are non-evaluable for DLTs will be allowed to continue in the study and receive CORT125281 in combination with enzalutamide. Patients who are non-evaluable for DLTs may be replaced to allow a sufficient number of patients to evaluate DLTs (Section 9.4.1).

After all patients complete 3 cycles of treatment or discontinue treatment, the data will be unblinded and the DRC will meet to review the safety and available PK and PD data. The DRC will evaluate the frequency of DLTs, the DLT rate (number of DLTs in DLT-evaluable patients per week [7-day period] during the DLT-evaluation period), and overall tolerability in their assessment of the dose titration regimen as the Phase 2 RD.

If the DLT rate for the regimen is $\geq 33\%$, alternative titration schemes may be considered as the regimen for the RD, such as greater time increments between dose escalations or limiting the upper range of the regimen to those dose levels corresponding to a DLT rate of $< 33\%$. Once the DRC has determined the RD, patients assigned to Arm B who have not experienced dose reductions due to toxicity will then escalate the CORT125281 dose per the recommended upward titration regimen.

